Frequency of caffeine Intake			
Infrequent (< 3 times per week)	60 (13.1)	152 (33.3)	212 (46.5)
Frequent (≥ 3 times per week)	168 (36.9)	76 (16.7)	244 (53.5)
Bedtime (hours)			
23:00 and before	24 (5.3)	137 (30.0)	161 (35.3)
After 23:00	204 (44.7)	91 (20.0)	295 (64.7)
Family history of menstrual disorders			
No	151 (33.1)	191 (41.9)	342 (75.0)
Yes	77 (16.9)	37 (8.1)	114 (25.0)
Age (years)			
Mean (SD)	22.0 (1.4)	21.0 (1.5)	21.5 (1.5)
Age at menarche (years)			
Mean (SD)	12.2 (1.5)	13.4 (1.7)	12.8 (1.7)
Marital status			
Never Married	206 (45.2)	221 (48.5)	427 (93.6)
Ever married	22 (4.8)	7 (1.5)	29 (6.4)
Place of participant's residence			

With family	17 (3.7)	44 (9.87)	61 (13.4)
At student dormitory	211 (46.3)	184 (40.3)	395 (86.6)
Father's educational status			
Secondary and above (> 5 y schooling)	180 (39.5)	212 (46.5)	392 (86.0)
Below secondary (0 – 5 y schooling)	48 (10.5)	16 (3.5)	64 (14.0)
Mother's educational status			
Secondary and above (> 5 y schooling)	168 (36.8)	191 (41.9)	359 (78.7)
Below secondary (0 – 5 y schooling)	60 (13.2)	37 (8.1)	97 (21.3)
Father's occupational status			
Formal occupation	130 (28.5)	142 (31.1)	272 (59.6)
Informal occupation	98 (21.5)	86 (18.9)	184 (40.4)
Mother's occupational status			
Formal occupation	65 (14.3)	44 (9.3)	109 (23.9)
Informal occupation	163 (35.7)	185 (40.6)	348 (76.1)

Outcome measures

Outcome measure information

In accordance with the study protocol, this section (Table 8) details the predefined primary outcomes used to evaluate intervention efficacy. The study focused on three key outcomes: dysmenorrhea, PMS and MI. Each was measured during the post-intervention period using standardized assessment tools. To support the study's quasi-experimental design and statistical analysis, all outcome variables were recoded as binary indicators.

Table 8. Summary of outcome measures information

Data elements	Dysmenorrhea	Premenstrual Syndrome (PMS)	Menstrual Irregularity (MI)
Outcome measure type	Primary	Primary	Primary
Outcome measure title	Prevalence of Dysmenorrhea	Prevalence of PMS	Prevalence of MI
Outcome measure description	Assessed according to Andersch and Milsom	Premenstrual symptoms were assessed using premenstrual	Menstrual irregularity was assessed based on

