Participants in the control group did not receive the BCC intervention or any related educational sessions but were matched with the intervention group based on number and baseline characteristics. Of the 249 participants initially enrolled in the control arm, 241 completed the outcome assessment interview. After data quality checks, 238 participants were retained for the final dysmenorrhea analysis. For the PMS and MI outcomes, 228 participants with complete and valid data were included in their respective analyses.

After propensity score matching, 98 matched participants from each group (n=196) were used for the final analysis of each outcome variable, ensuring balance between the groups on key covariates.

Analysis population information

This section provides (Table 9) an overview of the analysis populations for each outcome measure, including the number of participants at baseline and after propensity score matching. It also outlines the methods used to define the final samples included in the analyses.

Table 9. Overview of analysis population by groups for outcome measures

Outcomes	Group	Overall number of participants analyzed	Analysis population description
Dysmenorrhea	Intervention	234	Following initial recruitment and data quality verification, 234 participants in the intervention group and 238 in the control group were eligible for analysis. However, Final analyses were conducted using 1:1 propensity score matching without replacement and a caliper of 0.01, yielding a matched sample of 196 participants (98 from each group).
	Control	238	
	Total	472	
PMS and MI	Intervention	228	For both PMS and IMC outcome measures, 228 participants from each group provided valid and complete responses for the baseline analysis. Following 1:1 propensity score matching without replacement (caliper = 0.01), 98 participants per group were retained, yielding a final matched sample of 196.
	Control	228	
	Total	456	

Outcome measure data

Table 10 represents the outcome measure data for all participants who completed the follow-up assessment. Results are shown separately for the intervention and control groups, with each outcome reported as the number and percentage of participants. The data reflect the prevalence of each specified condition at follow-up, according to group assignment.

Table 10. Prevalence of key menstrual disorders among participants in control and intervention groups

Outcome variables	Control (n = 238)	Intervention (n = 234)	Total (N = 472)

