The intervention group attended BCC sessions on menstrual health, diet, and physical activity from May to June 2023, with bi-monthly follow-ups through January 2024. The control group did not receive any educational intervention. The dysmenorrhea outcome analysis included 234 participants from the intervention group and 238 from the control group. In the case of PMS and MI, 228 participants with complete and valid data were analyzed per group. To ensure baseline comparability, final analyses included 98 matched participants per group (n=196) after propensity score matching.

Total number affected by all-cause mortality

- Not applicable as the participants received the non-invasive nature of the behavioral intervention.

Total number at risk for all-cause mortality

- Not applicable as the participants received the non-invasive nature of the behavioral intervention.

Total number at risk for serious adverse events

- Not applicable as the participants received the non-invasive nature of the behavioral intervention.

Total number affected by any serious adverse event

- Not applicable as the participants received the non-invasive nature of the behavioral intervention.

Limitation and caveats

This quasi-experimental study lacked randomization, which may have introduced residual confounding and limited causal inference. About 4% of intervention participants missed sessions or follow-up, possibly underestimating the true effect. While the study aimed to reflect real-world settings by conducting sessions in academic institutions, potential confounding factors related to control group characteristics were not assessed. Dietary intake quantity was not measured, and 24-hour recalls may have been impacted by recall bias, affecting data accuracy.

Certain Agreements

Are all PIs employees of sponsor?

- Yes: The principal investigator (PI) is an employee of the sponsor

There were no agreements restricting the principal investigators from discussing, presenting or publishing the study results. The study was self-financed without external sponsorship.

Results point of contact

Name or official title: [name]. [name], principal investigator (PI) of the study

Organization name: Shahjalal University of Science and Technology, Sylhet, Bangladesh

[contact]

Email: [contact]

References

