- Method: Chi-squared, t-test, regression (logistic), conditional logistic regression
- Comments (Method): Pre- and post-PSM tests used Pearson's chi-square; conditional logistic regression applied to matched data; bivariate and multivariate logistic regression used for robustness checks

Method of Estimation

- Estimation Parameter: Odds Ratio (OR)
- Estimated Values: Reported as crude odds ratios (COR) and adjusted odds ratios (AOR). Coefficient value was used to estimate ATE and ATT (Table 11).
- Confidence Interval Level: 95%
- Number of Sides: 2-sided
- Lower and upper limit: Reported per outcome (see Table 11)

- Parameter Dispersion Type: Standard error of the mean
- Estimation Comments: Odds ratios compared the intervention group (numerator) to the control group (reference) for menstrual outcomes. Odds ratios reflect the likelihood of menstrual outcomes in the intervention group relative to the control group. ATE and ATT were also estimated using PSM.

Table 11. Estimated odds ratios from bivariate and multivariable (before matching) as well as conditional (after matching) and logistic regression models assessing the impact of the BCC module on menstrual health outcomes

Outcomes	Before matching		After matching
	COR (95% CI)	AOR (95% CI)	AOR (95% CI)
Dysmenorrhea	0.07 (0.04, 0.11)***	0.13 (0.06, 0.26)***	0.13 (0.05, 0.34)***
Premenstrual syndrome	0.07 (0.04, 0.11)***	0.13 (0.07, 0.23)***	0.12 (0.06, 0.27)***
Menstrual Irregularity	0.12 (0.07, 0.20)***	0.26 (0.14, 0.48)***	0.21 (0.09, 0.45)***

* Indicated chi square value define the level of significance i.e. * $p < 0.05$, ** $p < 0.01$, *** $p < 0.001$

Other statistical analysis

Additional scientifically appropriate analyses were conducted to ensure robustness and validity of the findings:

1. **Propensity Score Matching (PSM):** PSM was used to control for baseline differences between the intervention and control groups. Participants were matched 1:1 using nearest-neighbor matching with a caliper width of 0.01 and without replacement. Covariate balance was assessed using standardized mean differences (bias <10%) and post-matching chi-square tests.

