2. Sensitivity Analyses: To confirm the quality of matching and reduce potential bias, covariate balance diagnostics were conducted, including checks for percentage bias (<10%), variance ratios (acceptable range: 0.5–2.0), and visual inspection via kernel density plots to ensure common support. Bayesian logistic regression was also applied to estimate the Log Bayes Factor, comparing models with and without the intervention to assess the strength and consistency of effects.

3. Alternative Estimates of Treatment Effect: In addition to logistic regression models, the ATE and ATT were calculated (Table 12). These estimates served as supplementary measures and supported the stability of intervention effects across multiple analytical approaches.

Table 12. Estimated treatment effect of the BCC intervention on menstrual health outcomes via propensity score matching technique

Outcomes	Average treatment effect (ATE)		Average treatment effect on the treated (ATT)	
	Coefficient (95% CI)	p-value	Coefficient (95% CI)	p-value
Dysmenorrhea	−0.23 (−0.35, −0.11)	p < 0.001***	−0.27 (−0.40, −0.13)	p < 0.001***
Premenstrual syndrome (PMS)	−0.39 (−0.52, −0.25)	p < 0.001***	−0.42 (−0.57, −0.26)	p < 0.001***
Menstrual irregularity (MI)	−0.30 (−0.41, −0.18)	p < 0.001***	−0.31 (−0.45, −0.16)	p < 0.001***

* Indicated chi square value define the level of significance i.e. * p < 0.05, ** p < 0.01, *** p < 0.001

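### Table 10 prints impossible counts for menstrual irregularity, a primary outcome, and its group percentages use the pooled total, so the dysmenorrhea and PMS figures are about half the true group prevalences

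*Combined protocol and SAP*

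**What the plan says.** The protocol section on outcome measure information states: "The study focused on three key outcomes: dysmenorrhea, PMS and MI". Table 8 lists all three as primary, each titled as a prevalence.

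The section on outcome measure data introduces Table 10 as follows: "Results are shown separately for the intervention and control groups, with each outcome reported as the number and percentage of participants". It adds: "The data reflect the prevalence of each specified condition at follow-up, according to group assignment". The column heads carry the group sizes: 238 control and 234 intervention for dysmenorrhea, and 228 and 228 for PMS and MI. The group description under adverse event information gives the same sizes: "The dysmenorrhea outcome analysis included 234 participants from the intervention group and 238 from the control group", and "In the case of PMS and MI, 228 participants with complete and valid data were analyzed per group". No footnote to Table 10, 7A or 7B names a different base for the percentages.

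The MI rows of Table 10 read:

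| MI | Control (n = 228) | Intervention (n = 228) | Total (N = 456) |
|---|---|---|---|
| No | 118 (25.8) | 93 (20.4) | 323 (70.8) |
| Yes | 205 (45.0) | 23 (5.0) | 218 (29.2) |

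Table 11 in the SAP gives crude odds ratios before matching of 0.07 (0.04 to 0.11) for dysmenorrhea, the same for PMS, and 0.12 (0.07 to 0.20) for MI.

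**The concern.** Table 10 is the only place where the outcome counts by group appear. For MI, the rows and columns do not add up under the table's own headings, so neither the prevalence in each group nor the crude difference can be recovered. Read literally, 205 of 228 controls (90%) would be irregular.

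For dysmenorrhea and PMS the counts are sound, but the percentages are not what the text promises. Anyone who quotes them as prevalence by group roughly halves both the prevalence and the absolute difference.

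This can also mislead about what adjustment did. Suppose the coefficients in Table 12 are risk differences, which is an assumption because the scale is not stated. Subtracting the printed PMS percentages gives 26.8 points, which looks smaller than the adjusted effects (ATE -0.39, ATT -0.42). On group denominators the crude difference is 53.5 points, which is larger. For dysmenorrhea, subtraction gives 28.4 points, which looks close to the ATT of -0.27, whereas the crude difference by group n is 55.8 points.

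**Working it through.** **Inputs.** Counts, percentages and group sizes come from Table 10, crude odds ratios from Table 11, and baseline counts from Tables 7A and 7B.

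**1. Reproducing the printed percentages.** Count divided by pooled N gives:

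- Dysmenorrhea, N = 472: 29, 159, 209 and 75 give 6.1, 33.7, 44.3 and 15.9, all as printed.
- PMS, N = 456: 83, 205, 145 and 23 give 18.2, 45.0, 31.8 and 5.0, all as printed.
- MI, N = 456: 118, 93, 205 and 23 give 25.9 (printed 25.8), 20.4, 45.0 and 5.0.

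So the pooled N is the denominator for all twelve group cells.

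**2. Prevalence on group denominators.**

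| Outcome | Control | Intervention | Difference | Difference of printed percentages |
|---|---|---|---|---|
| Dysmenorrhea | 209/238 = 87.8% | 75/234 = 32.1% | 55.8 points | 44.3 - 15.9 = 28.4 |
| PMS | 145/228 = 63.6% | 23/228 = 10.1% | 53.5 points | 31.8 - 5.0 = 26.8 |

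The last column is my subtraction; the document does not print these differences.

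**3. MI sums.**

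- Control: 118 + 205 = 323, against 228.
- Intervention: 93 + 23 = 116, against 228.
- Total column: 323 + 218 = 541, against 456.
- No row: 118 + 93 = 211, printed 323.
- Yes row: 205 + 23 = 228, printed 218.
- 218/456 = 47.8%, printed 29.2%. The figure 29.2% corresponds to 133/456, and 456 - 323 = 133.

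**4. Crude odds ratios from the counts.** OR = (intervention Yes × control No)/(intervention No × control Yes), with a Wald interval on the log scale.

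- Dysmenorrhea: (75 × 29)/(159 × 209) = 0.065 (0.041 to 0.105). Agrees with Table 11.
- PMS: (23 × 83)/(205 × 145) = 0.064 (0.039 to 0.107). The interval agrees, but 0.064 rounds to 0.06, not the printed 0.07.
- MI as printed: (23 × 118)/(93 × 205) = 0.142 (0.086 to 0.237). Does not agree with 0.12 (0.07 to 0.20).

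**5. What the MI counts may have been (inference only).** The entries 118, 205 and 323 form a coherent No row: 118 + 205 = 323, and 25.8 + 45.0 = 70.8. Take 228 per group and 323 No in total, hence 133 Yes. Of all integer splits, only control 118 No/110 Yes with intervention 205 No/23 Yes reproduces all three Table 11 figures: 0.120 (0.073 to 0.199). The neighbouring splits, with 22 or 24 irregular in the intervention group, give 0.11 and 0.13. This would mean 110/228 = 48.2% against 23/228 = 10.1%. The search relies on the printed 323 being right, and 110 is printed nowhere, so this is not a source value.

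The stray values have possible origins elsewhere. The entry 93 (20.4) and the count 218 both appear in the dietary-diversity rows of Table 7B (218 there with 47.8%). The pair 205 (45.0) and 23 (5.0) is identical to the PMS intervention column of Table 10. Carry-over is possible but not shown.

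**6. Tables 7A and 7B.** 59 of 62 and 58 of 62 group percentages lie within 0.1 point of count/pooled N. The other seven match neither denominator and differ from count/pooled N by at most 0.35 point. For example, sedentary in Table 7A is printed as 43.6% against 24.2%, but by group n it is 206/238 = 86.6% against 114/234 = 48.7%. In Table 7B, mother's occupation sums to 44 + 185 = 229 in the intervention column and 109 + 348 = 457 overall. The percentages do not settle which count is off: 76.1% fits 347/456, while 40.6% fits 185/456. The printed 9.3% beside 44 equals 44/472, the entry for the same cell in Table 7A.

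**The case against.** The strongest reply is that the denominator is a matter of presentation. Cell percentages of the whole table are a legitimate quantity. Table 8 gives the data type as counts, the dysmenorrhea and PMS counts are complete, and the convention can be detected: 44.3 + 15.9 gives the 60.2 in the Total column, while the control column adds to only 50.4. This stands as far as recoverability goes, since the right figure is one division away. It does not rescue the description, because text, title and column heads all promise prevalence by group.

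On MI, the reconstruction suggests a fault in the display of Table 10 rather than in the data or the Table 11 model. That is plausible, and it limits the damage, but it remains inference. Text extraction from PDF could have moved 205 to another cell. It would not readily explain 218 beside 29.2%, or 93 in place of a count that completes 228, and the adjacent rows are intact.

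Two further objections are fair. The Table 12 comparison depends on an assumed scale and sets unmatched differences beside matching-based estimates, so it illustrates the consequence and carries no weight of its own. The PMS odds ratio, the mother's-occupation counts and the seven small percentage discrepancies are minor, and belong in the same clean-up.

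**Conclusion.** The concern holds. The MI block of Table 10 is impossible under its own headings: 323 and 116 against 228 each, totals of 541 against 456, and 218 beside 29.2%. Its crude odds ratio of 0.14 does not match the 0.12 in Table 11. All group percentages in Table 10 use the pooled N without saying so, which puts dysmenorrhea and PMS at about half their group prevalence. These findings rest only on printed figures.

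Whether the MI error arose in the source document or in the reading of the PDF cannot be settled here, and the 118/110 and 205/23 reconstruction needs source confirmation. The matched conditional logistic regression, which is the primary analysis, is not shown to be affected. In Tables 7A and 7B the denominator affects presentation only. The correction should be made, because wrong figures are stated for primary outcomes.

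**What to change.** - **MI in Table 10:** reconcile all six counts with source data, including whether 205 and 23 truly belong to MI or were carried over from PMS. Then compute group percentages on 228 per group, and check that the result reproduces 0.12 (0.07 to 0.20).
- **Dysmenorrhea and PMS in Table 10:** recompute the group columns on 238/234 and 228/228. Keep the pooled N for the Total column only, and state the denominator in a footnote.
- **Table 11:** check the PMS crude odds ratio, since the printed counts round to 0.06.
- **Tables 7A and 7B:** re-tabulate on group n, which also replaces the seven percentages that fit neither denominator. Check the mother's-occupation counts in 7B against source.

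The cost is re-tabulation for dysmenorrhea, PMS and Tables 7A and 7B, a source check for the MI and mother's-occupation counts, and a check of one entry in Table 11. No new data or new analysis is needed unless the MI source check turns up a discrepancy with the analysed dataset.

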Female students were recruited from three public universities in Bangladesh: Patuakhali Science and Technology University (PSTU), Barisal University (BU), and Khulna University (KU) for a BCC module on menstrual health from May 20 to June 30, 2023. Recruitment occurred via campus outreach and voluntary registration. University-approved session dates were held in campus venues. Follow-up occurred from July 15, 2023, to January 15, 2024. A post-intervention assessment was conducted from February to March 2024 through comparing the intervention group to the control group.

Pre-assignment details

Initially 498 participants (249/group) were recruited. Seven intervention participants were excluded before assignment for missing sessions/protocol violation, leaving 242. At six-month follow-up, 480 participants (239 intervention, 241 control) completed assessments as because 3 intervention and 8 control participants were excluded due to missed follow-up or withdrawal. After data checks, 8 were excluded for invalid dysmenorrhea data, leaving 234 intervention and 238 control (total 472 participants) for that outcome. For PMS and MI, 24 more were excluded (10

intervention and 14 control group), yielding 456 participants (228 per group). Propensity score matching (PSM) identified 196 matched participants (98 per group) for each of outcomes.

Group information

Two groups were assigned: an intervention group receiving the BCC module on menstrual health, and a control group with no intervention. Participants were female university students from PSTU, BU, and KU, Bangladesh, with group assignment based on attending at the BCC sessions.

Group title

1. Intervention Group
2. Control Group

Group description

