Started	249 (Intervention Group) 249 (Control group)	Intervention: participants who registered after informed consent and attended the first session of BCC module Control: Participant from the same universities were selected and listed after providing consent for the assessment study.	Intervention: first session attendance Control: Not exposed to the BCC intervention	249 (Intervention Group) 249 (Control group)
Completed	242 (Intervention Group)	Participants who attended all three intervention sessions.	Completed all sessions	242
Not completed	7 (Intervention Group)	Participants dropped out before completing the 2nd and/or 3rd session.	Protocol violation	7

Period 2: Follow-up phase

This was a six-month post-intervention follow-up period, during which participants in the intervention group received periodic support visits to reinforce behavioral changes and sustain the practices introduced during the BCC sessions (Table 2).

Table 2. Overview of participation status and milestone achievements in follow-up phase

Participation status	Data (number of participants)	Comments	Milestone title	Milestone data (number of participants)
Started	242 (Intervention Group)	Participants who completed all the sessions of the intervention and entered follow-up phase.	Follow-up initiated and available at first follow-up visit	242

Completed	239 (Intervention Group)	Participants available at 6-month follow-up assessment.	Follow-up completed	239
Not completed	3 (Intervention Group)	Participants lost to follow-up during the periodic monitoring visits conducted every two months.	Lost to follow-up	3

Period 3: Post-intervention evaluation

This period represents the final stage of the study to assess the effectiveness of the BCC module on key menstrual health outcomes through a quasi-experimental design using matched control and intervention participants (1:1 PSM) (Table 3, Table 4A and 4B). Outcome assessments were done for dysmenorrhea, PMS and MI.

Table 3. Participant flow and milestone completion in post-intervention outcome evaluation before matching

Participation status	Outcomes	Data (number of participants)	Comments	Milestone title	Milestone data (number of participants)
Started	Dysmenorrhea, PMS and MI	239 (Intervention), 241 (Control)	Participants agreed to join and assessed for final evaluation of outcomes	Assessment initiated	480

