Completed	Intervention	98	All 98 participants in the matched group successfully completed the post-intervention assessment.	Matching completion and final outcome analysis	196
	Control	98	The evaluation was completed by 98 matched control participants while the rest were excluded in accordance with the 1:1 matching and no-replacement criteria.		
Not completed	Intervention	130	As no matches within the caliper of 0.01 could be identified, the participants were excluded from the analysis	Participants were excluded as they did not fall within the region of common support.	260
	Control	130	Despite being within the common support region, these participants were excluded to maintain the 1:1 matching ratio and adhere to the no-replacement rule.		

Baseline characteristics

Group information

Group title

1. Intervention Group
2. Control Group

Group description

The intervention group included participants who attended all three sessions of the BCC module on menstrual health management. Initially, 249 participants were recruited, and 242 completed all sessions. At the six-month follow-up, 239 participants completed the outcome assessment. After data cleaning, 234 participants were eligible for the final analysis of the dysmenorrhea outcome, while 228 participants had valid data and were included in the analyses of PMS and MI.

Participants in the control group did not receive the BCC intervention but were matched in number and characteristics to the intervention group. Initially, 249 participants were listed for the control arm, and 241 completed the outcome assessment interview. Following data quality verification, 238 participants were included in the final analysis for the dysmenorrhea outcome. For the PMS and MI outcomes, 228 participants had valid and complete data and were included in the respective analyses.

After propensity score matching, 98 matched participants from each group (n=196) were used for the final analysis of each outcome variable, ensuring balance between the groups on key covariates.

Baseline analysis population information

The baseline analysis populations differ slightly from the initial recruitment numbers due to participant withdrawal, non-response, absence during sessions or protocol violation, and exclusion based on data quality checks for outcome variables (Table 5).

Table 5. Baseline Profile of Participants by Study Group: Intervention vs. Control

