Father's Education	Father's educational status	Education levels were categorized as: "Below secondary education" (no formal education, primary, or incomplete secondary schooling) and "Secondary or higher education" (completed secondary school, higher secondary, college, or university)	Count of participants	Not applicable	Below Secondary (0-5 y schooling) / Secondary and above(> 5 y schooling)	Participants
Mother's Education	Mother's educational status					
Father's Occupation	Father's occupational status	Occupational status was self-reported as either Formal (salaried or secure jobs) or Informal (homemaking, daily wage, or insecure work)	Count of participants	Not applicable	Formal / Informal	Participants
Mother's Occupation	Mother's occupational status					

Number of baseline participants

The number of baseline participants is the same as the overall number of baseline participants, as it includes all individuals who completed baseline data collection and met the data quality criteria.

Although PSM was later used to create comparable groups for outcome analysis, the baseline measures reflect the entire recruited sample before matching. Therefore, no separate or reduced sample size is reported in this section.

Baseline Measure Data

Baseline characteristics were assessed at the time of outcome evaluation for both the intervention and control groups. Although data were collected post-intervention, propensity score matching was applied to balance pre-existing covariates and reduce selection bias in estimating the treatment effect. The Table 7(A and B) present the baseline values for each measure across the intervention and control groups, as well as for the total study population.

Table 7A. Comparison of baseline characteristics between study groups for dysmenorrhea outcome

Variables	Control (n = 238)	Intervention (n = 234)	Total (N = 472)
Physical activity level			
Sedentary	206 (43.6)	114 (24.2)	320 (67.8)
Active and Athlete	32 (6.6)	120 (25.6)	152 (32.2)
BMI (kg/m²)			
Normal weight (18.5-22.9)	83 (17.6)	171 (36.2)	254 (53.8)
Underweight (<18.5)	44 (9.3)	37 (7.8)	81 (17.2)
Overweight and obese (>22.9)	111 (23.5)	26 (5.5)	137 (29.0)
MDD (scoring ≥ 5)			
No	153 (32.4)	96 (20.3)	249 (52.8)
Yes	85 (18.01)	138 (29.2)	223 (47.2)
Food craving for high fat and sweet food			
No	77 (16.3)	164 (34.8)	241 (51.1)

Yes	161 (34.1)	70 (14.8)	231 (48.9)
Skipping breakfast			
No	72 (15.5)	169 (35.8)	241 (51.1)

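### The roughly 4% of intervention women who missed sessions or follow-up are in no reported analysis, so the stated possibility that they led to an underestimate is unsupported; an overestimate among all who started the module is more likely

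*Combined protocol and SAP*

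**What the plan says.** Under Limitation and caveats the document states: "About 4% of intervention participants missed sessions or follow-up, possibly underestimating the true effect".

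The participant flow shows what happened to these women.

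- Pre-assignment details: "Initially 498 participants (249/group) were recruited". Then: "Seven intervention participants were excluded before assignment for missing sessions/protocol violation, leaving 242". At the six-month point, "3 intervention and 8 control participants were excluded due to missed follow-up or withdrawal".
- Table 1 counts 249 intervention women as started, defined as "participants who registered after informed consent and attended the first session of BCC module". It lists the 7 as not completed: "Participants dropped out before completing the 2nd and/or 3rd session".
- Tables 2 and 3 carry forward 242 and then 239 intervention women.
- Baseline characteristics, Group description: "The intervention group included participants who attended all three sessions of the BCC module on menstrual health management". The group description under Outcome measures repeats this condition.
- Number of baseline participants: "the baseline measures reflect the entire recruited sample before matching". Tables 7A and 7B cover 472 and 456 women.

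The SAP's Statistical analysis overview makes conditional logistic regression on the matched sample the primary analysis. The 98 matched intervention women are drawn from the 234 (dysmenorrhea) or 228 (PMS and menstrual irregularity) who remained.

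**The concern.** The limitation is a dilution argument: women who received less of the module pull the intervention group's result towards that of the controls. It works only if those women are counted in the intervention group. Here they were taken out.

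Once they are out, the question is how the excluded women would have compared with those who stayed. Women who stop attending a behavioural programme may well gain less from it. If so, their removal makes the effect look larger than it was among all who started. A limitations section tells readers which way the error is likely to run, and this sentence presents the result as conservative when the participant flow gives no basis for that.

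Two other wordings obscure the issue. Placing the exclusion of the 7 ahead of assignment makes it look like screening, while Table 1 shows women who had already started. Describing the baseline tables as covering everyone recruited hides that 26 or 42 of the 498 are absent.

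**Working it through.** **Inputs.** 249 per group enrolled, 7 session drop-outs, 3 intervention and 8 control women lost (Pre-assignment details, Tables 1 and 2). Data-quality exclusions from Table 3: dysmenorrhea 5 intervention and 3 control; PMS and menstrual irregularity 11 and 13. (Pre-assignment details gives 10 and 14 for the latter; only Table 3's split leads to 228 per group.) Outcome counts from Table 10: dysmenorrhea 75/234 against 209/238; PMS 23/228 against 145/228.

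**1. The stated 4%.** (7 + 3)/249 = 10/249 = 4.0%. Reproduced.

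**2. Are the 10 women in any analysis?**
- Dysmenorrhea: 249 - 7 - 3 - 5 = 234.
- PMS and menstrual irregularity: 249 - 7 - 3 - 11 = 228.

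Both chains close exactly on the analysed numbers, so none of the 10 is in the unmatched analyses. The matched women are a subset of these, so none is in the primary analysis either.

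**3. Adding the 10 back to the unmatched comparison.** Risk difference (RD) = intervention proportion minus control proportion. The 10 outcomes are not given, so the whole range is shown, with the control rate as one assumed value in between.

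| Assumption for the 10 | Dysmenorrhea RD | PMS RD |
|---|---|---|
| As analysed (10 left out) | 75/234 - 209/238 = -0.558 | 23/228 - 145/228 = -0.535 |
| None affected | 75/244 - 209/238 = -0.571 | 23/238 - 145/228 = -0.539 |
| Affected at the control rate | 83.8/244 - 209/238 = -0.535 | 29.4/238 - 145/228 = -0.513 |
| All affected | 85/244 - 209/238 = -0.530 | 33/238 - 145/228 = -0.497 |

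For dysmenorrhea the effect shrinks if 4 or more of the 10 were affected (79/244 = 32.4%, against 32.1% as analysed) and grows if 3 or fewer were (78/244 = 32.0%). For PMS, 1 affected leaves it virtually unchanged (24/238 = 10.1%, against 10.1%), and 2 or more shrink it.

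**4. Bounds on all 249 per group.** Missing outcomes are 249 - 234 = 15 intervention and 249 - 238 = 11 control for dysmenorrhea, and 249 - 228 = 21 per group for PMS. The worst case counts missing intervention women as affected and missing controls as unaffected; the best case does the reverse.
- Dysmenorrhea: worst (75 + 15)/249 - 209/249 = -0.478; best 75/249 - (209 + 11)/249 = -0.582.
- PMS: worst (23 + 21)/249 - 145/249 = -0.406; best 23/249 - (145 + 21)/249 = -0.574.

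These bounds also include the women removed for invalid data, who are not part of the 4%.

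**5. Menstrual irregularity.** The Table 10 rows do not add up to 228 per group. Assuming 323 regular of 456 (the printed 70.8%) and 23 irregular in the intervention group, the controls have 456 - 323 - 23 = 110 irregular. The crude odds ratio is then (23/205)/(110/118) = 0.12, as in Table 11. On that assumption the RD is -0.382 as analysed, and between -0.386 and -0.344 with the 10 added back.

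**6. One-sidedness.** Losses to follow-up or withdrawal were 3 intervention and 8 control women. Only the 7 session drop-outs (7/249 = 2.8%) have no counterpart, because controls had no sessions to attend.

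**7. Baseline sample.** 498 - 472 = 26 and 498 - 456 = 42 women are missing from Tables 7A and 7B.

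**The case against.** The limitation is hedged, and the outcomes of the 10 women are unknown. A reader might infer that the direction of bias is proven to be the reverse of what is stated, or that restoring the women could only shrink the effect. Neither follows: with few or none of the 10 affected, the effect grows slightly. This objection stands. It does not rescue the sentence, because the hedge still points one way and the document gives no reason to expect the excluded women to have done better than those who stayed. Reading the true effect as that of full attendance does not help either, since a group made up only of completers is not diluted for that target.

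A reader might also infer that the completer population was concealed. It was not: two group descriptions state the attendance condition and Table 1 gives 242 and 7. What is missing is the consequence for what the estimate means.

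Nor were exclusions confined to the intervention group, since 8 controls were also dropped for missed follow-up or withdrawal. And restoring the 10 does not give the effect of offering the module. The 249 had registered voluntarily and attended session 1, and no count of students offered it appears.

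Assignment is said to rest on attendance, which could explain why the 7 are placed ahead of it. That reading conflicts with Table 1, where they had started. The phrase about the entire recruited sample is qualified nearby, where the text restricts the sample by data quality and Tables 5 and 7 print each N. That part is loose wording.

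Finally, all the figures are crude, while the primary analysis is matched. That is correct and limits what the bounds can show.

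**Conclusion.** The concern holds for the stated direction of bias. The women behind the 4% are in no reported analysis and cannot dilute the effect, so the suggestion of an underestimate is unsupported. Relative to all women who started, an overestimate is more likely if the excluded women benefited less. That condition is an assumption, though a plausible one.

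The size is small. Adding the 10 back moves the crude risk difference by at most 2.8 percentage points towards a smaller effect for dysmenorrhea and 3.8 for PMS, or by 1.3 and 0.4 points the other way. Even the worst case on 249 per group leaves large crude differences (-0.478 and -0.406), so no crude conclusion reverses.

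This rests on the 4% being the 7 plus 3, the only counts in the flow that match. It says nothing about the size of any shift in the matched estimate: covariates were recorded at the outcome evaluation, which these women did not enter, so as described they could not be given a propensity score.

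**What to change.** 1. Replace the limitation. State that the intervention estimate applies to women who completed all three sessions and were followed up, and that excluding the others may overstate the effect among all who started. Do not extend this to students offered the module.
2. Reconcile the timing given for the 7 exclusions in Pre-assignment details with Table 1, which counts these women as started after session 1.
3. Reconcile the description of the baseline sample under Number of baseline participants with the 472 and 456 women tabulated.
4. Add the best-case/worst-case bound on all 249 per group (dysmenorrhea -0.582 to -0.478; PMS -0.574 to -0.406), labelled as a bound on the unmatched comparison and not on the matched primary estimate. Add menstrual irregularity once its Table 10 rows are corrected.

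The cost is a few sentences and a short calculation from existing counts; no new data are needed. The downside is that the worst-case figures are less favourable than the reported ones.
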